## 12.6 Follow-up Evaluations for All Patients

The following evaluation should be performed at least annually, until death or withdrawal of consent as described for:

- Survival: contact by telephone or in-person visit; Methods used for attempted contact must also be documented properly.

(For Group A, contact should occur after end of treatment visit; for Group B, contact should occur prior to or after disease progression; survival contact for patients in Group C should continue until death or withdrawal of consent.)

## 12.7 Calendar of Clinical and Laboratory Evaluations

|   | Baseline | Every 4 weeks
(±5 days) | Every 12 months
(±30 days) | Off-Treatment A | Follow-up B |  |  |  |  |  |
|---|----------|----------------------------|-------------------------------|----------------------------|------------------------|--|--|--|--|--|
| (Group A)
thalidomide
(THALOMID®)  |          | Once daily A    |                               |                            |                        |  |  |  |  |  |
| Informed consent  | X        |                            |                               |                            |                        |  |  |  |  |  |
| Eligibility   | X        |                            |                               |                            |                        |  |  |  |  |  |
| Physical exam   |          |                            | X                             | X                          |                        |  |  |  |  |  |
| CBC w/diff, plts  |          |                            | X                             | X                          |                        |  |  |  |  |  |
| CMP   |          |                            | X                             | X                          |                        |  |  |  |  |  |
| Lactate dehydrogenase (LDH)   |          |                            | X                             | X                          |                        |  |  |  |  |  |
| Beta-HCG (WoCBP)  |          | X A             | X A                | X                          |                        |  |  |  |  |  |
| Adverse event evaluation  |          | X A             |                               |                            |                        |  |  |  |  |  |
| Survival  |          |                            |                               |                            | X B         |  |  |  |  |  |
| Footnote(s):   |          |                            |                               |                            |                        |  |  |  |  |  |
| A To be done only for patients in Group A                                      |          |                            |                               |                            |                        |  |  |  |  |  |
| B Contact by telephone or in-person visit until death or withdrawal of consent |          |                            |                               |                            |                        |  |  |  |  |  |

## 13.0 MEASUREMENT OF EFFECT

For the purposes of this study, patients should be evaluated for response every as per standard of care until documented disease progression or study withdrawal (for reasons including toxicity and/or death).

### 13.1 Definitions

| Response Category            | Physical Exam                          | Lymph Nodes             | Lymph Node Masses       | Bone Marrow            |
|------------------------------|--|-------------------------|-------------------------|------------------------|
| CR                           | Normal                                 | Normal                  | Normal                  | Normal                 |
| CR (u)                       | Normal                                 | Normal                  | Normal or >75% decrease | Normal indeterminate   |
| PR                           | Normal                                 | Normal or ≥50% decrease | Normal or ≥50% decrease | Positive or irrelevant |
| Relapse/ Progressive Disease | Enlarging liver, spleen or other sites | New or increased        | New or increased        | Reappearance           |

Key: CR=Complete Response; CR(u)=Complete Response/unconfirmed; PR=Partial Response

### 13.2 Response Criteria

#### 13.2.1 CR requires the following:

1. Complete disappearance of all detectable clinical and radiographic evidence of disease and disappearance of all disease-related symptoms if present before therapy, and normalization of those biochemical abnormalities (e.g. LDH) definitely assignable to NHL.
2. All lymph nodes and nodal masses must have regressed to normal size. Previously involved nodes that were between 1.1 to 1.5 cm in their greatest transverse diameter before treatment, must have decreased to ≤ 1 cm in their greatest transverse diameter after treatment, or by more than 75% in the sum of the products of the greatest diameters (SPD).
3. The spleen, if considered to be enlarged before therapy on the basis of a CT scan, must have regressed in size and must not be palpable on physical exam. However, no normal size can be specified because of the difficulties in accurately evaluating splenic and hepatic sizes.
4. If the bone marrow was involved by lymphoma before treatment, the infiltrate must be cleared on repeat bone marrow aspirate and biopsy on the same site.

#### 13.2.2 CR/unconfirmed (CR (u)) requires the following:

1. Residual lymph node mass greater than 1.5 cm in greatest transverse diameter that has regressed by more than 75% in the SPD. Individual nodes that were previously confluent must have regressed by more than 75% in their SPD compared with the size of the original mass.
2. Indeterminate bone marrow (increased number or size of aggregates without cytologic or architectural atypia).

#### 13.2.3 PR requires the following:

1. > 50% decrease in SPD of the six largest dominant nodes or nodal masses.

2. No increase in the size of other nodes, liver, or spleen.
3. Splenic or hepatic nodules must regress by at least 50% in the SPD.
4. With the exception of splenic and hepatic nodules, involvement of other organs is considered assessable and not measurable disease.
5. Bone marrow assessment is irrelevant for the determination of a PR because it is assessable and not measurable disease.
6. No new sites of disease.

13.2.4 Stable disease (SD) is defined as less than a PR but not progressive disease.

13.2.5 Relapsed disease (PD) requires the following:

1. Appearance of any new lesion or increase by  $\geq 50\%$  in the size of previously involved sites.
2.  $\geq 50\%$  increase in greatest diameter of any previously identified node greater than 1 cm in its short axis or in the SPD of more than one node.

13.2.6 Progressive disease (PR or nonresponders) require the following:

1.  $\geq 50\%$  increase from nadir in the SPD of any previously identified abnormal node for PRs or nonresponders.
2. Appearance of any new lesion during the end of therapy.

### 13.3 (Duration of Overall Response)

(The duration of overall response is measured from the time measurement criteria are met for CR or PR (whichever is first recorded) until the first date that recurrent or progressive disease is objectively documented (taking as reference for progressive disease the smallest measurements recorded since the treatment started)).

The duration of overall CR is measured from the time measurement criteria are first met for CR until the first date that recurrent disease is objectively documented.)

### 13.4 (Duration of Stable Disease)

(Stable disease is measured from the start of the treatment until the criteria for progression are met, taking as reference the smallest measurements recorded since the treatment started.)

### 13.5 Progression-Free Survival (PFS)

Patients will be followed at a minimum of annual intervals (every 12 months,  $\pm 30$  days) or as clinically indicated and at the discretion of the Investigator to document the progression-free interval.

### 13.6 Overall Survival (OS)

Patients will be followed at annual intervals to document the overall survival.

## 14.0 ADVERSE EVENTS

The descriptions and grading scales found in the revised NCI Common Terminology Criteria for Adverse Events (CTCAE) version 3.0 will be utilized for adverse event reporting.

### 14.1 Purpose

Adverse event data collection and reporting, which are required as part of every clinical trial, are done to ensure the safety of patients enrolled in the studies, as well as those who will enroll in future studies using similar agents. Adverse events are reported in a routine manner at scheduled times during a trial. Additionally, certain adverse events must be reported in an expedited manner for timelier monitoring of patient safety and care.

### 14.2 Adverse Event

Adverse Event (AE): Can be any unfavorable and unintended sign (e.g., an abnormal laboratory finding), symptom, or disease temporally associated with the use of a drug, medical treatment, or procedure without judgment about causality. An adverse event can arise from any use and from any route of administration, formulation, or dose including an overdose. This includes any newly occurring event or a previous condition that has increased in severity or frequency since initiation of a drug, medical treatment, or procedure.

#### Abnormal Findings

In any clinical assessment, a value outside the normal or reference range (such as a clinical laboratory, vital sign, or ECG) will not be reported or assessed as an AE unless that value is considered to be of clinical significance by the investigator. A value of clinical significance is one that leads to discontinuation or delay in protocol treatment, dose modification, therapeutic intervention\*, or is considered to be a clinically significant new finding or change from baseline by the investigator.

\*Transfusion support administered to offset clinical symptoms of anemia or thrombocytopenia will not be considered therapeutic intervention.

#### Signs and Symptoms

Signs/symptoms resulting from an underlying clinical diagnosis should be documented as one comprehensive AE. If no underlying clinical diagnosis can be identified, each sign/symptom should be reported as a separate independent event. (A new or worsening event resulting from an underlying clinical diagnosis or a reaction to concurrent medications should be documented as a separate independent AE unless it is within the normal range of fluctuation for that patient.)

Grade Changes/Fluctuations

AEs will be reported at the maximum grade/severity experienced for the duration of the event. Should one particular event warrant further investigation, additional details may be collected at the discretion of the Principal Investigator.

Progression of Disease

Progression of disease, if documented in accordance to standard of care, should not be reported as an AE.

Tests and Procedures

Tests and procedures should not be reported as AEs. The underlying clinical diagnosis (or sign/symptom in the event an underlying clinical diagnosis is not known) requiring testing or a procedure, should be reported as an adverse event if it meets criteria for reporting.

#### 14.3 Serious Adverse Events (see also Appendix A)

Serious AE (SAE) means any untoward medical occurrence that occurs at any dose:

- 1. Results in death.**
- 2. Is life-threatening.**

The term "life-threatening" in the definition of "serious" refers to an event in which the patient was at risk of death at the time of the event; it does not refer to an event which hypothetically might have caused death if it were more severe).

- 3. Requires inpatient hospitalization or prolongation of present hospitalization.**  
Elective hospitalization to simplify protocol treatment/evaluations or to treat a baseline condition that did not worsen from baseline will not be considered an SAE.
- 4. Results in persistent or significant disability/incapacity.**  
Disability is defined as a substantial disruption of a person's ability to conduct normal life functions.
- 5. Is a congenital anomaly/birth defect.**
- 6. Is a medically important event.**

A medically important event may not be immediately life threatening or result in death or hospitalization but may jeopardize the patient or may require intervention to prevent one of the other outcomes listed in the definition above, or involves suspected transmission via a medicinal product of an infectious agent. Examples of such medical events include allergic bronchospasm requiring intensive treatment in an emergency room or at home, blood dyscrasias or convulsions that do not result in inpatient hospitalization, or the development of drug dependency or drug abuse; any organism, virus, or infectious particle (e.g., prion protein transmitting Transmissible Spongiform Encephalopathy), pathogenic or nonpathogenic, is considered an infectious agent.

Clarification should be made between the terms *serious* and *severe* because they ARE NOT synonymous. The term *severe* is often used to describe the intensity (severity) of a specific event (as in mild, moderate, or severe myocardial infarction); the event itself, however, may be of relatively minor medical significance (such as a severe headache). This is NOT the same as *serious*, which is based on patient/event outcome or action criteria described above and is usually associated with events that pose a threat to a patient's life or functioning. A severe AE does not necessarily need to be considered serious. For example, persistent nausea of several hours duration may be considered severe nausea but not an SAE. On the other hand, a stroke resulting in only a minor degree of disability may be considered mild but would be defined as an SAE based on the above noted criteria. Seriousness (not severity) serves as a guide for defining regulatory reporting obligations.

#### 14.4 Adverse Event Collection Period

In this protocol, adverse events include only treatment-emergent adverse events. A treatment-emergent adverse event (TEAE) is defined as any event that begins or worsens after the start of protocol treatment. All baseline-emergent adverse events, any event that begins or worsens after completion of the informed consent but prior to the start of protocol treatment, should be reported as a Baseline/Comorbid Condition.

All adverse events that occur within  $\leq$  30 days of the last dose of study therapy will be reported and followed until resolution. Resolution is defined as a return to baseline status or the stabilization of an event with the expectation that it will remain chronic. (Exception: If a patient begins an alternative therapy that confounds accurate assessment of AEs within  $\leq$  30 days of the last dose of study therapy, all adverse event collection will stop and any ongoing events will be left open.)

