## PROTOCOL SYNOPSIS

|                                    |   |
|------------------------------------|---|
| Protocol Title              | Long-term Follow-Up and/or Continued Thalidomide (THALOMID®) Maintenance Therapy for Patients Enrolled on Clinical Trial 20030165   |
| Targeted Patient Population | Patients enrolled on Clinical Trial 20030165.   |
| Study Design                | 
The study is designed to provide long-term follow-up and/or to offer continued maintenance thalidomide (THALOMID®) therapy to those patients enrolled in 20030165.
 
Group A: Patients who achieved CR in 20030165 and continue to receive maintenance Thalidomide.
 
Group B: Patients who achieved CR in 20030165, but are not receiving maintenance Thalidomide.
 
Group C: All other patients enrolled in 20030165 who expired or experienced disease progression.
 |
| Treatment Schema            | Thalidomide (THALOMID®) will be administered as per standard of care guidelines to Group A; in compliance with REMS™ program requirements.  |
| Study Duration              | 
Patients in Group A, B and C will be followed until withdrawal of consent, or death.
 
Note: All other patients in Group C who expired on 20030165 will also be included in all analyses.
  |
| Follow-up Required          | All patients will be followed annually by telephone or in-person visit(s), until death or withdrawal.   |
| Objectives                  | 
Primary Objective: To provide long-term follow-up and/or offer continued maintenance thalidomide (THALOMID®) to patients enrolled in 20030165 .
 
Secondary Objective: To continue to evaluate objectives specified for 20030165 (please refer to 20030165 for details).
  |
| Expected Number of Patients | 
Group A: 2
 
Group B: 12
 
Group C: 8
   |
| Expected Number of Centers  | 1-Sylvester Comprehensive Cancer Center (SCCC)
Note: SCCC is inclusive of the constituent satellite sites.  |

|  |  |
|--|--|
| Expected Duration of the Protocol | At least 5 years.  |
| Inclusion Criteria                | 

1. Enrolled on the 20030165 clinical trial.

2. Ability to understand and willingness to sign a written informed consent document.

  |

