## 7.0 STUDY DESIGN

The study is designed to provide long-term follow-up, as well as to offer continued thalidomide (THALOMID®) maintenance therapy to patients enrolled in 20030165.

There are 14 eligible patients in Groups A and B expected to rollover from 20030165. An additional Group C consisting of all other patients who expired or experienced disease progression on 20030165, will also be included in all analyses.

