#### 8.4.1 *Concurrent Medications*

Concurrent medications will not be captured as part of this trial.

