##### Venous and Arterial Thromboembolism:

An increased risk of venous thromboembolism (such as deep vein thrombosis and pulmonary embolism), ischemic heart disease (including myocardial

infarction), and stroke have been reported in patients with multiple myeloma treated with thalidomide [see Venous and Arterial Thromboembolism].

Peripheral Neuropathy:

Peripheral neuropathy is a very common, potentially severe, adverse reaction of treatment with thalidomide that may result in irreversible damage. Peripheral neuropathy generally occurs following chronic use over a period of months. However, reports following relatively short-term use also exist. Incidence of neuropathy events leading to discontinuation, dose reduction or interruption increases with cumulative dose and duration of therapy. Symptoms may occur sometime after thalidomide treatment has been stopped and may resolve slowly or not at all.

Somnolence, dizziness, and rash are the most commonly observed adverse reactions associated with the use of thalidomide. Adverse event profiles from clinical trials are summarized in the sections that follow.

Adverse Reactions in Multiple Myeloma Controlled Clinical Trials

The safety analyses were conducted in two controlled clinical studies (Study 1 and Study 2). The safety analysis in Study 1 was conducted on 204 patients who received treatment. Table 1 lists the most common adverse drug reactions ( $\geq 10\%$ ). The most frequently reported adverse reactions were fatigue, hypocalcemia, edema, constipation, sensory neuropathy, dyspnea, muscle weakness, leukopenia, neutropenia, rash/desquamation, confusion, anorexia, nausea, anxiety/agitation, tremor, fever, weight loss, thrombosis/embolism, neuropathy-motor, weight gain, dizziness, and dry skin.

Twenty-three percent of patients (47/204) discontinued due to adverse reactions; 30% (31/102) from the THALOMID/dexamethasone arm and 16% (16/102) from the dexamethasone alone arm.

Table 1: Adverse Drug Reactions Reported in  $\geq 10\%$  of Patients in the THALOMID/Dexamethasone Arm

| (Study 1 - Safety Population; N=204) |                         |                    |                       |                    |                    |
|--------------------------------------|-------------------------|--------------------|-----------------------|--------------------|--------------------|

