## **APPENDIX A: EXPEDITED ADVERSE EVENT (AE) REPORTING REQUIREMENTS**

For all AEs that meet criteria for expedited reporting, the Principal Investigator (PI) is obligated to pursue and provide follow-up reporting information until the event has resolved or until an acceptable medical endpoint has been reached (i.e. for the duration specified in the protocol), or the patient is lost to follow-up.

The PI and all applicable research study team members should become familiar with the safety profile of the investigational agent(s) and/or intervention at the start of the study and for the duration of the research, e.g. by reviewing the Investigator's Brochure (IB) and any Safety Reports released, (i.e. by the Sponsor) as applicable.

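### Section 14.4 stops all adverse-event collection once a confounding alternative therapy begins, with no exemption for serious, thalidomide-related or expedited events, and its baseline rule does not fit patients already on thalidomide

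*Protocol*

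**What the plan says.** Section 14.4 of the Protocol restricts adverse events to treatment-emergent ones, meaning "any event that begins or worsens after the start of protocol treatment". A separate class, "any event that begins or worsens after completion of the informed consent but prior to the start of protocol treatment", is recorded as a baseline or comorbid condition.

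After the last dose, events arising in the next 30 days are reported and followed to resolution, with one exception. If in that period the patient starts an alternative therapy that confounds the assessment of events, "all adverse event collection will stop and any ongoing events will be left open". The exception does not distinguish serious from non-serious events, or related from unrelated ones.

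The only group on drug is Group A, which the Synopsis describes as "Patients who achieved CR in 20030165 and continue to receive maintenance Thalidomide". Two such patients are expected.

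Appendix A says that, for events meeting expedited criteria, the principal investigator "is obligated to pursue and provide follow-up reporting information until the event has resolved". The sentence goes on to allow an acceptable medical endpoint or loss to follow-up instead, and a parenthesis ties the period to whatever the protocol specifies.

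**The concern.** Two features of Section 14.4 do not suit this study.

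- **The stop rule is total.** A confounding new therapy is a reason for caution about attribution. It is a weaker reason to stop recording serious events, suspected pregnancy, or events already judged related to thalidomide. The Protocol itself warns, for peripheral neuropathy in Section 9.1.4: "Symptoms may occur sometime after thalidomide treatment has been stopped and may resolve slowly or not at all". The days just after stopping are therefore not free of drug-related harm.
- **The baseline rule is written for patients starting a drug.** It assumes an untreated interval between consent and first dose. Group A has none, because these patients arrive on thalidomide from 20030165.

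Toxicity is a listed secondary endpoint (Section 3.2), and the Data and Safety Monitoring Committee reviews adverse-event data (Section 16.1). What is at stake is whether the safety record for the few on-drug patients is complete and correctly labelled.

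**Working it through.** The plan gives no event rate, no consent-to-start interval and no frequency of subsequent therapy, so there is no figure to reproduce. The check sets the provisions side by side.

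**1. Stop rule against the other collection rules**

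| Provision | What it requires | Fit with the Section 14.4 exception |
|---|---|---|
| 14.5 | Serious events, expected or not, and suspected pregnancy in Group A are targeted for collection; no exception stated | Conflicts: 14.4 stops them too |
| 12.2.1 | Group A events monitored and collected throughout the study | Conflicts: 14.4 ends collection earlier |
| 17.4 | Source documents must record, at minimum, action taken and resolution for adverse events | Conflicts: 14.4 leaves ongoing events open |
| Appendix A | Expedited events followed to resolution, an acceptable medical endpoint or loss to follow-up, for the protocol's duration | Unreconciled: the text does not say which governs |

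**2. Cases under a literal reading**

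- A serious event that began on thalidomide is still unresolved when a confounding therapy starts. Section 14.4 leaves it open; Section 17.4 requires its resolution to be documented.
- Section 12.5 schedules a serum pregnancy test for women of childbearing potential 30 days (±5) after the last dose. If a confounding therapy has already begun, a positive result arrives after collection has stopped. Section 14.5 still calls for it.
- If the confounding therapy starts on day d after the last dose, 30 − d days of the window are lost. The documents give no d, so the loss can be anything from 30 days down to 0.

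**3. Baseline rule against Group A**

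The Protocol does not define when protocol treatment starts for someone already on drug. There are two readings.

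- *First dose under this protocol.* Events between consent and that dose happen on thalidomide but are filed as baseline or comorbid. Section 3.2.1, by contrast, defines evaluability for toxicity by events occurring while the patient receives thalidomide.
- *Original start under 20030165.* The interval is empty and the sentence has no effect for Group A.

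Either way, the rule needs a definition or replacement for this group.

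**4. Scale**

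- Groups A and B: 2 + 12 = 14, which agrees with Section 7.0: "There are 14 eligible patients in Groups A and B expected to rollover from 20030165".
- One Group A patient with truncated or misfiled events is 1/2 = 50% of the on-drug group.
- With no affected patient among n, the one-sided 95% upper bound on the rate is 1 − 0.05^(1/n). For n = 2 it is 1 − 0.05^(1/2) = 77.6%; for n = 1 it is 1 − 0.05 = 95%.

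These bounds show only that two patients cannot support a useful rate. The value of the safety data lies in complete individual cases. The figures do not measure an under-count.

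**The case against.** Stopping collection once a confounding therapy begins is a deliberate, stated choice, and later events are hard to attribute. That explains the exception for non-serious, unrelated events. It does not explain the silence on serious events, which Section 14.5 wants collected without qualification. Section 12.2.1 sits among the on-treatment evaluations and might be read as ending with treatment, which would weaken that one conflict. Sections 14.5 and 17.4 carry no such limit.

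Several stronger readings are tempting, and the documents do not support them.

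- *Any new therapy stops collection.* It does not. The therapy must confound event assessment and start within the 30-day window.
- *Section 14.4 flatly contradicts Appendix A.* Appendix A covers only expedited events, accepts endpoints other than resolution, and can be read as deferring to the period set in Section 14.4. The two are unreconciled, which is less than contradictory.
- *The trigger cannot be recorded because of Section 8.4.1.* That section says "Concurrent medications will not be captured as part of this trial". A therapy begun after the last thalidomide dose is not clearly concurrent, and the fields of the off-treatment and follow-up forms in Appendix B are not shown.
- *On-drug events are certainly misfiled.* This depends on an undefined start. The interval may be short or empty, baseline events are still recorded, and any that worsen after the start become treatment-emergent.
- *The toxicity endpoint is biased toward safety.* The direction is plausible, but no size or probability can be derived. The Protocol does not say how often stopping thalidomide leads to another therapy within 30 days.
- *The rule explains why late neuropathy would be missed.* Only in part. Neuropathy beginning after day 30 falls outside collection with or without the exception.

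**Conclusion.** The point holds in limited form. Followed literally, Section 14.4 drops serious, thalidomide-related and expedited events inside the Protocol's own 30-day window once a confounding therapy starts. This conflicts with Sections 14.5, 12.2.1 and 17.4 and is unreconciled with Appendix A. The baseline rule also does not fit Group A; whether it mislabels on-drug events depends on reading the start of protocol treatment as the first dose under this protocol.

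The effect is confined to safety reporting in about 2 patients and cannot be quantified. Section 15.0 plans no formal analysis, so no test or estimate is at risk. This is a minor point, worth correcting because the repair is cheap.

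**What to change.** In Section 14.4:

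1. Limit the alternative-therapy exception to non-serious events not related to thalidomide. Serious events, suspected pregnancy and thalidomide-related events are then still collected to day 30 and followed as in Appendix A. Record the start date of the alternative therapy.
2. For Group A, count as treatment-emergent any event that begins or worsens after consent.

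Then reconcile Sections 12.2.1, 14.5 and 17.4 and Appendix A with this text, including which section sets the follow-up period for expedited events.

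The cost is about two sentences and one case report form field for about 2 patients. It changes data capture only, not treatment. The downside is that some late events will be confounded by the new therapy; the five attribution categories in Section 14.6, from definite to unrelated, can handle that.
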